## 4 Study Methods

### 4.1 General Study Design and Plan

The study design is a multicentre, parallel, individually randomized, controlled diagnostic trial in consecutive HIV positive adults admitted to hospital in selected sites of Mozambique and Tanzania.

Schedule of Visits.

	Day 0 (recruitment )	Day 0 (recruitment) Intervention arm	Day 0-3 (<72h)	Daily	At discharge If discharged before day 28/56	Week 4 +/- 3 days	Week 8
Control arm							
Baseline Evaluation							
Informed consent	X	X					
Eligibility criteria verified	X	X					
CD4 count / Viral Load &	X	X					
Locator information	X	X					
Brief medical history	X	X					
Proof of HIV status stored	X	X					
WHO Symptom screening	X	X			X		
TB Investigations							
	Urine AlerelAM# Sputum Ultra*	Sputum Ultra Stool/rectal swab Ultra Urine Ultra Urine AlerelAM 2x Oral Swabs Urine FujiLAM Blood CD4 Blood for CRP					
Samples collected and tests							
Results issued				X			
Further contacts							
Verification TB diagnosis / ad hoc TB investigations				X	X	X	X
Verification TB treatment initiation				X	X	X	X
Verification vital status				X	X	X	X
HIV care / ART				X	X	X	X

## 4.2 Inclusion-Exclusion Criteria and General Study Population

This study has the following inclusion and exclusion criteria.

### Inclusion criteria:

1. Adults 18 years or older.
2. Confirmed HIV infection (including both antiretroviral (ART)-naïve and experienced).
3. Admitted to the hospital (adult medical wards) at the time of enrolment.

### Exclusion criteria:

1. Unable to provide informed consent (if no authorized relatives are in the position to provide the consent).
2. Living outside the catchment area of the participating hospital(s).
3. With plans to migrate outside the catchment area within 2 months after recruitment.
4. Currently receiving anti-TB therapy or having received anti-TB therapy in the last 6 months prior to enrolment.
5. Receiving preventive TB treatment in the preceding 6 months
6. Participants admitted for traumatic reasons, acute abdomen, delivery or pregnancy (maternal conditions), or for planned/scheduled surgery.
7. Referred from other hospital
8. Positive result to a SARS-CoV-2 test (RT-PCR, antigen test, or other similar test that might define COVID-19 case in the study site)\*

### Study population

The study population will be adult ( $\geq 18$  years) PLHIV participants admitted to hospital and living in the catchment areas within the 4 district hospitals in Tanzania and Mozambique, regardless of presence of TB compatible symptoms.

## 4.3 Randomisation and Blinding

This is an individually randomized clinical trial. Eligible participants will be randomized to either the intervention or control arm, with 50% of participants in each of the arms. Randomization will be conducted using a web-based application <https://odk-central.finddx.org/-/x/6RPyVJQoEjzOPUd3qHIRQYX6MtFnnwq> that can be used on any smartphone device with internet connection. The day of randomization for each participant will be the enrolment day (study Day 0). At the time a participant is randomized, the study staff enters in the application several key data (patient study number and date of birth) and in reply, the allocated randomized arm is provided a few seconds later in the same application interface. Thus, internet connection is needed for randomizing participants. Pre-registered users of the study team will be allowed to use the randomization application.

Developing a reliable training plan by which study teams (at the clinic and at the lab) are fully aware of the diagnostic allocation is critical so that arm-specific testing can be implemented without mistakes in a timely manner. This includes careful strategic measures (posters, signs, weekly meetings, etc) as part of the site internal planning, which also need to consider staff shifts, holidays (both in the hospital and at the laboratory). A screening and randomization log need to be daily updated. Day 0 CRF needs to be data entered in a timely manner to allow the central monitoring of number of recruited subjects per arm, site and week and overall mapping of participants included in the study.

This is an unblinded trial. Neither participants, nor study staff will be blinded to tests practiced or test results.

#### 4.4 Study Variables

The Baseline participants variables we will collected from TB-CAPT-HIV EXULTANT-BaselineCharacteristics-v3, and the following versions of this document. From this CRF the important variables for the analysis are:

Variable		Used in
Label	name	
Date of enrolment	ENROL_D	To calculate endpoints related to time.
Time of enrolment	ENROL_T	To calculate endpoints related to time.
Country	COUNTRY	To adjust some regression models.  For previous analysis about at random lost to follow up.
Sex	SEX	To describe the participant's profile.  For previous analysis about at random lost to follow up.
Ethnic group	ETHNIC ETHNIC_SPEC	To describe the participant's profile.  For previous analysis about at random lost to follow up.

Level of education	EDUCATION EDUCATION_SPEC	To describe the participant's profile.  For previous analysis about at random lost to follow up.
Employment Status	EMPLOYMENT EMPLOYMENT_SPEC	To describe the participant's profile.  For previous analysis about at random lost to follow up.
Type of Employment:  2.6 Is the patient employed as a health care worker?  2.7 Is the patient employed as a prison warder/work at a correctional facility?  2.8 Is the patient employed as a miner?	EMPL_HLTH_YN  EMPL_PRSN_YN  EMPL_MINE_YN	To describe the participant's profile.  For previous analysis about at random lost to follow up.
Early HIV positive result  3.1.1 Date of earliest HIV positive result:	HIV_POS_DATE	To describe the participant's profile.  For previous analysis about at random lost to follow up.
Current taking antiretroviral	ART_YN	To describe the participant's profile.  For previous analysis about at random lost to follow up.
Previous TB episodes	TB_TX_YN	To describe the participant's profile.  For previous analysis about at random lost to follow up.
Received BCG vaccination	BCG_YN	To describe the participant's profile.  For previous analysis about at random lost to follow up.

Participant live alone?		To describe the participant's profile.  For previous analysis about at random lost to follow up.
Patient taking cotrimoxazole?	CTX_YN	To describe the participant's profile.  For previous analysis about at random lost to follow up.
High blood pressure	HIGH_RR_YN	To describe the participant's profile.
Diabetes	DIABETES_YN	To describe the participant's profile.
Cardiac disease	CARDIAC_YN	To describe the participant's profile.
Epilepsy	EPILEPSY_YN	To describe the participant's profile.
Karnofsky Performance Status Scale	KARNOFSKY	To describe the participant's profile.  For previous analysis about at random lost to follow up.
Patient's WHO clinical Stage	WHO_STAGES	To describe the participant's profile.  For previous analysis about at random lost to follow up.
TB treatment start	TB_TX_START_YN	To describe the participant's profile.  For previous analysis about at random lost to follow up.
Random group	RANDOM_ASSIGN	For previous analysis about at random lost to follow up.
Date of randomization	RANDOM_D	To calculate endpoints related to time.

The Follow-up week4 participants variables will be collected from TB-CAPT-HIV EXULTANT-Week-4-v3 CRF, and the following versions of this document. From this CRF the important variables for the analysis are:

Variable		Used in
label	name	
Is the visit taking place? (y/n)	W4_VISIT_YN	To calculate the number of people who come to visit at week 8
Is the visit taking place?, date	W4_VISIT_D	To calculate the time in the study, to draw the study K-M graphs in group of people who come to this visit.
If the patient has died, date of death	W4_DEATH_D	To use in the K-M graphs as an endpoint for these participants.
Has the patient started TB treatment since discharge?	W4_TB_TX_YN	To calculate the proportion of main study objective
Has the patient started TB treatment since discharge?, date	W4_TB_TX_START_D	To calculate the proportion of people started on treatment.
Has the patient abandoned TB treatment since last visit?	W4_TB_TX_END_YN	To calculate the failure TB treatment

The Follow-up week8 participants variables will be collected from TB-CAPT-HIV EXULTANT-Week-8-v3 CRF, and the following versions of this document. From this CRF the important variables for the analysis are:

Variable		Used in
label	name	
Is the visit taking place? (y/n)	W8_VISIT_YN	To calculate the number of people who come to visit at week 8

Is the visit taking place? (date)	W8_VISIT_D	To calculate the time in the study, to draw the study K-M graphs in group of people who come to this visit.
If the patient has died, date of death	W8_DEATH_D	To use in the K-M graphs as an endpoint for these participants.
Has the patient started TB treatment since discharge?	W8_TB_TX_YN	To calculate the proportion of main study objective
Has the patient started TB treatment since discharge?, date	W8_TB_TX_START_D	To calculate time at risk
Has the patient abandoned TB treatment since last visit?	W8_TB_TX_END_YN	To calculate the failure TB treatment

From Hospitalization Assessment TB-CAPT-HIV EXULTANT-Hospitalization assessment-v3, and the following versions of this document we will use for the analysis the next variables:

Variable		Used in
label	name	
Date of enrolment	ENROL_D	To calculate the participant's start time
Time of enrolment (24h format)	ENROL_T	
Date of discharge	HOSP_END_D	To calculate the participant's hospitalization time
Time of discharge (24h format)	HOSP_END_T	
Date of lab result: Sputum Ultra	SP_XP_RES_RECEPT_D	To calculate the time to obtain the laboratory results and classify the primary outcome $\leq 72$ h or $> 72$ h for Sputum Ultra sample
Time of lab result: Sputum Ultra	SP_XP_RES_RECEPT_T	

Date of lab result: Urine Ultra	URINE_XP_RES_RECEPT_D	To calculate the time to obtain the laboratory results and classify the primary outcome <= 72h or > 72h for Urine Ultra sample
Time of lab result: Urine Ultra	URINE_XP_RES_RECEPT_T	
Did the patient have cough during hospitalization?	HOSP_COUGH_YN	We will use to describe symptoms.  We will use as a factor variable in modelling
Did the patient have fever (>38°C) during hospitalization?	HOSP_FEVER_YN	We will use to describe symptoms.  We will use as a factor variable in modelling
Did the patient have night sweats during hospitalization?	HOSP_NIGHT_SWEATS_YN	We will use to describe symptoms.  We will use as a factor variable in modelling
Did the patient lose weight during hospitalization?	HOSP_WEIGHT_LOSS_YN	We will use to describe symptoms.  We will use as a factor variable in modelling
Was TB treatment initiated during hospitalization?	HOSP_TB_TX_YN	To calculate the primary objective variable, start treatment within 72h of enrolment
TB treatment initiated, Date and Time	HOSP_TB_TX_START_D HOSP_TB_TX_START_T	
If Yes, AND the patient has a microbiologically confirmed TB diagnosis (question 2.3), was the treatment initiated within 72hrs of enrolment?	HOSP_TB_TX_72H_YN	To determine the proportion of microbiologically confirmed TB cases starting treatment within 72 hours

If wasn't the treatment initiated within 72hrs of enrolment, reason	HOSP_TB_TX_72H_RSN HOSP_TB_TX_72H_RSN_SPEC	To determine the reasons behind starting treatment failure
---	---	--

The laboratory results we will be collected from (15) TB-CAPT-HIV EXULTANT-LabResults-v3- CRF, and the following version of this document. From this source we will select to study the following variables:

Variable		Used in
Label	name	
Date of sample collection	SAMP_COL_D	To check the range of dates in context of our research objectives
CD4 results	CD4_RES	To analyse the primary objective stratified by this variable
Viral load results	VL_RES	To analyse the primary objective stratified by this variable
Sputum Xpert Ultra	SP_XP_RES	To determine whether a patient is microbiologically confirmed
Urine Xpert Ultra	URINE_XP_RES	To determine whether a patient is microbiologically confirmed
Stool Xpert Ultra	STOOL_XP_RES	To determine whether a patient is microbiologically confirmed
Xpert Ultra in another specimen I	S1_XP_RES	To determine whether a patient is microbiologically confirmed
Xpert Ultra in another specimen II	S2_XP_RES	To determine whether a patient is microbiologically confirmed

The AlereLAM Results will come from the TB-CAPT-HIV EXULTANT-AlereLAM & CRP v3 form, and the update versions of this document. From this CRF will be get:

Variable		Used in
Label	name	
AlereLAM result	ALERE_RES	To determine whether a patient is microbiologically confirmed To do the sensibility analysis of test
If results available, date	ALERE_RES_D	To calculate the lab results time
If results available, time	ALERE_RES_T	
If results not available, reason	ALERE_RES_YN_RSN	To calculate the proportion and reasons of no AlereLAM result

The Study Completion participants variables we will collected from TB-CAPT-HIV EXULTANT-StudyCompletion-v3 form, and the following versions of this document. From this CRF the important variables for the analysis are:

Variable		Used in
Label	name	
Did participant complete the study procedures at study visit week 8?	VISIT_WK8_D	To calculate the proportion of endpoints at week 8
Did participant complete the study procedures at study visit week 8? date	VISIT_WK8_D	To calculate the time in the study, to draw the study K-M graphs
If not, and the participant withdrew, was withdrawn, dropped out or died during the study, indicate the primary reason	END_RSN	To calculate the proportion deaths, lost to follow-up, withdraws and complete study

Date participant completed, withdrew, was withdrawn/excluded or dropped out from study, date	END_D	To calculate the time in the study, to draw the study K-M graphs
--	-------	--

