8.1 Primary Endpoint(s)

The primary endpoint is:

- The proportion of participants diagnosed with microbiologically confirmed TB and started on TB treatment within 72 hours of enrolment, separately for intervention and control arm. The numerator is the number of participants per study arm who are diagnosed with microbiologically confirmed TB and start on treatment within 72 hours of enrolment. The denominator is the number of participants enrolled per study arm. We will compare this indicator between both study arms. Patients are defined to have microbiologically confirmed TB if at least one confirmatory TB test (Ultra, AlereLAM) gives a positive result.

Hospitalized PLHIV experience high mortality and TB underdiagnosis and misdiagnoses are frequent. TB diagnosis is important when you can quickly start appropriate therapy. This endpoint will capture both diagnostic dimensions of the intervention (higher rates of *Mtb* laboratory confirmation) as well as the relevant patient outcome (TB treatment initiated).

Diagnostic procedures and treatment initiation (if appropriate) should be completed within 72 hours of enrolment given the intervention is aimed at rapid collection of samples for all patients upon admission and that Ultra testing can provide results within a few hours from specimen collection at all participating sites.

The numerator of the primary endpoint also includes patients whose bacteriological confirmation might arrive after 72 hours of enrolment. There might be cases where liquid or solid culture might be requested and results arrive after 72 hours. If the patient had been put on treatment empirically (before a positive culture results has arrived), that case will contribute to the numerator, given that treatment would have been started in a "true" TB case.

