The primary efficacy endpoint has a composite numerator 'microbiologically confirmed TB and therapy initiated within 72 hours from admission' (success), 'non lab-confirmed TB or therapy

This project is part of the EDCTP2 programme supported by the European Union

not initiated within 72 hours' (failure).

Microbiological confirmation may arrive later than 72 hours after enrolment (to account for scenarios in which culture is requested or there is any delay on sample processing).

The primary efficacy analysis will be compared between the proportion of microbiologically confirmed TB and therapy initiated within 72 hours of enrolment in each study arm.

Adjustment for other variables (country, hospital, seasonality or other possible confounders) may be considered and will be described in detail in the analysis plan.

Missing values will be examined in detail. We may consider a multiple imputation procedure if necessary (variables with more than 10% of missing values).

We will accept as significant difference the p-values less than 0.05.

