## 7.2 Derived variables

We will create some derived variables according to solve the study hypothesis, some of them we will describe in the following SAP versions.

The variables that we will create are:

New Variable	Type	Values
Type of Employment	Categorical	0: Unemployed for any reason 1: Health care worker 2: Prison warder or work at a correctional facility 3: Miner
Time from last HIV+ result	Continuous	0 to randomization date
Time of follow-up	Continuous	From randomization date to end study completion date
Time to TB treatment initiation (in hours)	Continuous	From randomization date to start TB treatment date
ITT cohort	Categorical	0: Not included in ITT 1: Included in ITT
ATP cohort	Categorical	0: Not included in ATP 1: Included in ATP
Participants diagnosed with microbiologically confirmed TB	Categorical	0: No 1: Yes
Participants diagnosed with microbiologically confirmed TB and started on TB treatment within 72 hours of enrolment	Categorical	0: No 1: Yes
CD4 (binary)	Categorical	0: CD4 count <100

	1: CD4 count >=100
--	--------------------

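### The SAP is internally inconsistent on whether the 72 h limit in the primary endpoint covers Ultra results, and late culture counts in the protocol's text but is not listed in its definition of confirmed TB

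*SAP*

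**What the plan says.** **Late results, protocol.** Protocol 8.1 states: "The numerator of the primary endpoint also includes patients whose bacteriological confirmation might arrive after 72 hours of enrolment". Protocol 13.2.2 (efficacy analysis) repeats it: "Microbiological confirmation may arrive later than 72 hours after enrolment".

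**Late results, SAP.** SAP 3.4.1, 7.2 and 8.1 join confirmation and treatment and then give a single 72 h limit. The derived variable in SAP 7.2, for example, reads "Participants diagnosed with microbiologically confirmed TB and started on TB treatment within 72 hours of enrolment". None of the three says whether a result after 72 h still counts. In the hospitalization table of SAP 4.4, the receipt date and time of urine Ultra are to be used to "classify the primary outcome <= 72h or > 72h for Urine Ultra sample", and sputum Ultra has the same entry. The same table also holds the treatment start date and time and a form question: "If Yes, AND the patient has a microbiologically confirmed TB diagnosis (question 2.3), was the treatment initiated within 72hrs of enrolment". The stated use of that question is "To determine the proportion of microbiologically confirmed TB cases starting treatment within 72 hours".

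**Result variables in SAP 4.4.** Each Ultra result in the laboratory table has the use "To determine whether a patient is microbiologically confirmed", with no time limit. The AlereLAM result date and time have only the use "To calculate the lab results time".

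**Culture.** The protocol synopsis, Protocol 8.1 and SAP 3.4.1 define microbiological confirmation as at least one positive Ultra or AlereLAM. Protocol 8.1 then adds to the numerator a participant treated empirically whose culture turns positive later, and Protocol 13.2.2 names the culture scenario again. SAP 4.4 lists no culture variable.

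**The concern.** Protocol 13.2 leaves the details of the analysis to the SAP, so an analyst will build the primary variable from SAP 4.4 and 7.2. Someone who follows the receipt-time notes would score as a failure a participant who began treatment within 72 h and whose only positive Ultra came back later. The protocol scores that participant as a success. Someone who follows the treatment-time entries would agree with the protocol.

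For culture, the protocol's own definition and its explanatory text give different numerators, and the SAP as written has no variable with which to apply the explanatory text.

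This is the primary numerator of an unblinded trial (Protocol 10.6), so its derivation should be settled in writing before the data are analysed.

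**Working it through.** **1. How each rule scores a participant**

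| Participant | Protocol 8.1 text | Receipt-time notes in SAP 4.4 | Treatment-time entries in SAP 4.4 |
|---|---|---|---|
| Treated ≤72 h, positive sputum or urine Ultra received ≤72 h | success | success | success |
| Treated ≤72 h, only positive is sputum or urine Ultra received >72 h | success | failure | success |
| Treated ≤72 h, only positive is stool or other-specimen Ultra, late | success | cannot be applied: no receipt time listed | success |
| Treated ≤72 h, only positive is a later culture | success | no variable listed | no variable listed |
| Treated >72 h | failure | failure | failure |

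The second row is where the SAP disagrees with itself. The fourth is where Protocol 8.1 disagrees with its own definition, which lists only Ultra and AlereLAM.

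**2. Could a receipt cut be applied evenly?** SAP 4.4 lists six confirmatory results: Ultra on sputum, urine, stool, other specimen I and other specimen II, plus AlereLAM.
- Receipt time tied to the primary outcome: 2 (sputum and urine Ultra).
- No receipt time listed: 3 (stool and the two other specimens).
- Time listed, but only for laboratory turnaround: 1 (AlereLAM).

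2 + 3 + 1 = 6. Urine Ultra is scheduled in the intervention arm only (Protocol 11, SAP 4.1), so half of the cut falls on a test that the control arm does not have.

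**3. Who is exposed?** Protocol 10.9.1 aims for collection within 24 h and allows 72 h. Protocol 12 targets an Ultra result within 24 h of collection.
- Both targets met: 24 + 24 = 48 h at the latest, so the cut changes nothing.
- Collected between 48 and 72 h and reported on target: received as late as 72 to 96 h, so possibly cut.
- Collected after 72 h, which Protocol 10.9.2 still allows: always received late.

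To be reclassified, a participant must also have been treated within 72 h and have no timely positive on any other test. AlereLAM is due within two hours of collection (Protocol 12). Culture is not scheduled in either arm; Protocol 8.1 says only that it may be requested.

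**4. Scale.** The planned size reproduces. The pooled-variance formula for 19% against 26%, two-sided 5%, 80% power, gives 558 per arm, and 558 × 1.05 = 585.9, so 586. With that denominator:
- one participant: 100/586 = 0.17 points in that arm;
- six participants: 600/586 = 1.02 points.

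These are unit conversions. The documents give no frequency of late or culture-only confirmation, so no effect can be estimated.

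**The case against.** The strongest reply is that the protocol has already fixed the late-result rule, twice, and nothing in the SAP revokes it. The receipt-time reading rests on two notes in a variable list. SAP 3.4.1, 7.2 and 8.1 apply no receipt cut, and other entries in the same table time treatment. The receipt times also have a natural home: the per-protocol set in SAP 6.1.1 requires results within 72 h, and SAP 8.1 analyses the primary endpoint in that set too. Most of this stands. It shows which reading was probably meant, but the notes name the primary outcome, not the per-protocol set, and should be corrected.

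Four stronger readings are tempting and are not supported:
- *The SAP overturns the protocol.* It contains entries on both sides, so it is inconsistent, not opposed.
- *The definition excludes culture.* It does not list culture; no passage rules it out.
- *Culture results will not be captured.* SAP 4.4 selects variables for analysis. Protocol 10.10 records any additional TB investigation and its result, and the laboratory form in Protocol 14.2 can be used for additional tests.
- *Late results have no outer limit.* None is stated, but Protocol 14.2 ties the laboratory form to the study period and Protocol 10.11 ends participation at week 8.

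A reader might also infer a loss of power. Any such figure needs an assumed share of cases removed, which the documents do not give, and it would start from 19% and 26%, which are confirmation rates and not rates of the composite endpoint.

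**Conclusion.** The point holds as an error to correct. Two notes in SAP 4.4, taken literally, contradict the protocol's late-result rule and the SAP's own treatment-time entries. The protocol's inclusion of later culture does not match the definition of confirmation in either document, and the SAP as written cannot carry it out.

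The late-result half is a failure to carry over a rule that the protocol has already set. The culture half is undecided in the protocol itself. The effect on the result is probably small, because few participants are likely to be treated within 72 h with their only positive late or by culture; that is a judgement from the timing targets, not an estimate. The direction is unknown. The correction is worth making because it concerns the primary numerator and costs little.

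**What to change.** 1. In SAP 3.4.1, 7.2 and 8.1 state one derivation. Success = (treatment start date-time − enrolment date-time) ≤72 h, from ENROL_D/T and HOSP_TB_TX_START_D/T, and at least one qualifying positive result, which may arrive after 72 h, up to the week 8 study end.
2. In SAP 4.4 remove the reference to classifying the primary outcome from the sputum and urine Ultra receipt rows. Keep those times for the SAP 6.1.1 per-protocol set, and list stool and other-specimen receipt times for that set as well. Protocol 13.2.3 describes a different set, which also conditions on treatment within 72 h, so the two should not be cited as one.
3. Reconcile culture before analysis: either add it to the definition in both documents and to SAP 4.4, or remove it from Protocol 8.1 and 13.2.2.
4. Minor: SAP 7.2 derives hours to treatment from dates, so use date plus clock time. Where Protocol 13.2.2 counts the 72 h from admission, align it with enrolment, as used elsewhere in that section. A start after discharge has only a date on the week 4 form (SAP 4.4), so the derivation should say how that is handled, identically in both arms.

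The cost is wording in the SAP and one protocol clarification, plus possibly a source look-up for some receipt times or culture results. Enrolment and in-hospital treatment date-times are already listed.
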